5.1. LY2157299 – Nonclinical and Clinical Experience

5.1.1. *Nonclinical Pharmacokinetics of LY2157299*

Nonclinical pharmacokinetic (PK) studies were performed in 2 species, rat and dog. LY2157299 exposure was examined in rats following daily oral doses of 15, 50, and 150 mg/kg after 1 dose and 28 doses. The PK of LY2157299 were linear, but female rats had a consistently higher (approximately 2-fold) exposure over the course of the study. LY2157299 is rapidly absorbed and eliminated with a half-life ($t_{1/2}$) of approximately 4 to 8 hours.

As determined by metabolism studies in rats, most of LY2157299 was excreted in feces. Three metabolites have thus far been identified. The function and activity of these metabolites have not been defined at this time.

In the nonrodent studies using dogs, a gastric pH-dependent variability was observed suggesting that at acidic pH, LY2157299 had a less variable exposure. To reduce possible PK variability, LY2157299 will be administered on an empty stomach.

Male and female Fischer 344 (F344) rats were given daily oral doses of LY2157299 monohydrate at 0, 15, 50, or 150 mg/kg for 1 month. Male and female beagle dogs were given daily oral doses of LY2157299 monohydrate at 0, 50, 250, or 500 mg/kg for 1 month. The potential for induction of hepatic microsomal drug-metabolizing enzymes was evaluated by quantitating total cytochrome P450 (CYP) content in liver samples collected at necropsies. Slight but variable changes in total CYP content were observed in treated male rats, while no significant changes were observed in treated female rats. No statistically significant changes in total CYP content were observed in treated beagle dogs. The magnitude of the changes observed in male rats and the lack of significant change in female rats and male and female dogs suggest that LY2157299 is not an inducer of overall CYP content under the conditions of these studies.

The ability of LY2157299 to inhibit CYP-mediated metabolism in vitro was examined. The data show that LY2157299 would not be expected to inhibit metabolism mediated by CYP2D6, CYP2C19, CYP2C9, and CYP1A2. LY2157299 was found to competitively inhibit the biotransformation of midazolam to 1'-hydroxymidazolam, a marker activity for CYP3A4,

yielding an inhibition constant (K_i) value of 44 μM . LY2157299 was found to competitively inhibit the biotransformation of testosterone to 6 β -hydroxytestosterone, a marker activity for CYP3A4, yielding a K_i value of 290 μM .

Based on the nonclinical metabolism studies, LY2157299 is not anticipated to have the potential to accumulate in patients or have a risk of high hepatic metabolism.

For details on the nonclinical PK of LY2157299, please see the Investigator's Brochure (IB).

5.1.2. Nonclinical Pharmacokinetic/Pharmacodynamic Model

Because regular assessment of pSMAD in tumor tissue in patients is both too invasive and likely to produce variable results given the heterogeneous nature of tumor tissue, a specific bioassay was developed to determine pSMAD levels in a surrogate tissue, peripheral blood mononuclear cells (PBMC) (data on file, Eli Lilly; Farrington et al. 2007). To compare the effect of LY2157299 between the surrogate and tumor tissue, the pSMAD level changes measured in both PBMC and 4T1 tumor tissue in rats treated with LY2157299 was investigated. A significant relationship between pSMAD modulation in tumor cells and in peripheral blood was observed at 30- and 300-mg/kg doses (p-values were 0.002 and 0.059 in the 30- and 300-mg/kg groups, respectively, and <.0001 for the combined data) which suggests that the pSMAD modulation in human PBMC should be a useful surrogate of the pharmacodynamic (PD) effect of LY2157299.

A PK/PD model was developed to characterize the relationship between drug concentrations and pSMAD levels. This PK/PD model integrated the time course of the PK of the compound, the inhibition of pSMAD in tumor and PBMC, as well as the nonclinical tumor growth delay of 3 tumor animal models. This model was used to predict an anticipated dose range that is likely to be biologically effective in patients with cancer. The simulations from the rat and the mouse suggest that a range of 200 to 500 mg (total daily doses), administered twice daily are expected to produce the required percentage inhibition of pSMAD that has been associated with tumor-growth delay in the preclinical studies.

For details refer to the IB.

5.1.3. Clinical Pharmacokinetics of LY2157299

As of 19 August 2011, 39 patients have been treated with LY2157299 in an ongoing study, Study H9H-MC-JBAH (JBAH). Of 39 patients, noncompartmental PK analysis has been performed on 37 patients.

Results from all 5 cohorts showed rapid absorption of LY2157299, as demonstrated by measurable plasma concentrations at the first sampling time (0.5 to 2 hours). At steady state, on Day 14, the median time to maximum concentration ($t_{\text{max,ss}}$) ranged from 0.5 to 2 hours postdose, independent of dose. Both the maximum observed concentration at steady state ($C_{\text{max,ss}}$) and exposure increased with dose. The geometric mean of the apparent clearance at steady state (CL_{ss}/F) was similar across Cohorts 3, 4, and 5, whereas for the first 2 cohorts the scheduled sampling time was only up to 8 hours post dose and the parameter could not be estimated with any degree of certainty. No accumulation of LY2157299 in the 5 cohorts was

observed over the 14-day twice-daily (BID) dosing regimen, with accumulation ratio (RA) observed to be approximately 1. A population PK model, based on Cohorts 1 through 5 data, was developed. A first order absorption linear 2-compartment model, with elimination from the central compartment provided the best fit to the plasma data. The mean population clearance of LY2157299 was 38.4 L/h with standard error, expressed as a percentage coefficient of variation of 8% and the steady state volume of distribution (V_{ss}) was 193 L. From the population PK analysis of all 5 cohorts' data, the between-patient variance was estimated to be 46% on the population apparent clearance. The between-occasion variability on apparent CL was estimated at 18%.

The dose-proportionality analysis was performed for the PK parameters area under the plasma concentration-time curve from 0 to infinity ($AUC[0-\infty]$) and $C_{max,ss}$ (Day 15) using results from 30 patients from all 5 cohorts (pooled across Cycles 1 and 2 for Cohorts 3, 4, and 5). From this analysis, there was no evidence of a difference between Cycles 1 and 2 for Cohorts 3, 4, and 5. The estimated ratios of geometric means for $AUC(0-\infty)$ and $C_{max,ss}$ between 150 mg BID and 20 mg BID were estimated as 7.90 (90% CI: 2.85, 22.0) and 3.56 (90% CI: 2.09, 6.06), respectively. For a doubling of dose, the fold increases for $AUC(0-\infty)$ and $C_{max,ss}$ are 2.04-fold with corresponding 90% confidence limits (1.43, 2.89) and 1.55-fold with 90% confidence limits (1.29, 1.86), respectively. Within- and between-patient coefficients of variation were estimated as 26% and 40% for $AUC(0-\infty)$ at steady state, respectively, and 34% and 56% for $C_{max,ss}$, pooled across the 5 cohorts from the dose-proportionality analysis.

For additional information see Section 6.1 in the IB.

5.1.4. Nonclinical Toxicology of LY2157299

The toxicity of LY2157299 has been characterized in repeat- and intermittent-dose nonclinical safety studies up to 6 months duration in the rat and dog. The following paragraphs summarize the major findings in rats and dogs.

The heart and great vessels are major target organs for toxicity in both F344 rats and beagle dogs following treatment with LY2157299. These effects include valvulopathy and vascular lesions of multiple blood vessels at the base of the heart in rat and dog, which in the rat appear to be partially reversible. In the rat, a continuum of changes in the gastrointestinal tract have been described, including inflammation of the mucosa, simple mucosal hyperplasia, and adenocarcinoma following 6 months of continuous treatment. Based on safety pharmacology studies, administration of LY2157299 produced increases in hexobarbital-induced sleep time. Administration of LY2157299 may produce dose-dependent hemodynamic side effects, measured by decreased blood pressure and increases in heart rate, which can be easily monitored in the clinic and are reversible upon cessation of treatment. The nonclinical data do not reveal any substantive clinical risk of QT/QTc prolongation at doses that result in total plasma concentrations of at least 3.3 $\mu\text{g/mL}$.

LY2157299 was negative in a bacterial mutation test (Ames test) and an in vivo mammalian test (mouse micronucleus). However, LY2157299 was positive in an in vitro mammalian test

(chromosome aberration) with and without S9 activation. This positive finding is considered acceptable in the intended patient population.

Rats were dosed up to 3 months intermittently or 6 months continuously at 50, 150, and 250 mg/kg. Dogs have been dosed with up to 500 mg/kg for 1 month and 8, 20, and 60 mg/kg daily for 6 months. LY2157299 caused mortality in the rat at progressively lower doses as the duration of treatment increased. In shorter-duration studies, mortality was observed in rats administered 1200 mg/kg of LY2157299 in a 14-day pilot study and in the 3- and 6-month rat studies, mortality occurred in animals receiving daily doses of 150 (6-month study) and 250 mg/kg (3- and 6-month study) beginning on Days 83 and 54, respectively. All preterminal deaths in rats were attributed to compound-related inflammation of the aorta and distributing arteries at or near the base of the heart, except for 1 male for which the cause of death was undetermined and 1 male that died of an intestinal adenocarcinoma (6-month study). One female dog in the high-dose reversibility group (500 mg/kg) died shortly after the treatment phase ended in the 1-month study; death was attributed to bile peritonitis. There was no mortality observed in the 6-month dog study. Vascular lesions in the rat were characterized by minimal-to-severe inflammation of multiple blood vessels at the base of the heart including the ascending aorta, coronary arteries, and distributing arteries of the aortic arch. These changes were described in the 3-month (150 and 250 mg/kg) and 6-month (≥ 50 mg/kg) continuous-dose groups. The vascular damage in rats administered ≥ 150 mg/kg continuously for 3 and 6 months and 2 weeks on/2 weeks off correlated with serum chemistry and hematologic responses typical of chronic hemorrhage and inflammation. In rats given 150 and 250 mg/kg (mid and high dose, 6 months and ≥ 3 months, respectively), vascular inflammation was, in some animals, associated with vascular rupture resulting in acute hemorrhage into the thoracic cavity and death.

The no-observed-effect level (NOEL) for vascular damage in the rat is 50 mg/kg administered on a 2-weeks-on/2-weeks-off schedule. Changes in the base of the ascending aorta, characterized by minimal-to-marked degeneration, disorganization, and separation of intramural elastic laminae without an accompanying inflammatory response, were observed in the dog administered daily doses of 8, 20, or 60 mg/kg for 6 months. The aortic mural degeneration was focally extensive or multifocal with no compound-related microscopic changes in the descending aorta. Although the microscopic changes likely compromised regional aortic structural integrity, there were no diagnostic changes of an aortic aneurysm – no gross dilation, no effects in the intimal layer, and a lack of free blood within the wall of the aorta. A cardiac valvulopathy, characterized by endothelial/stromal cell proliferation, inflammation, and increases in smooth muscle actin immunolabeling and hemorrhage was identified in rats and dogs given high doses of LY2157299 for ≤ 30 days. In the 3- and 6-month studies, compound-related valvulopathy of similar character occurred at lower doses than previously described in studies ≤ 30 days in duration (150 and 250 mg/kg [intermittent 2 weeks on/2 weeks off and continuous groups] in the 3-month study and at all doses [50, 150, and 250 mg/kg] in the rat 6-month study and at the mid and high doses [20 and 60 mg/kg] in the dog). The cardiac valvulopathy observed in rats and dogs given LY2157299 were observed but have not been associated with extracardiac evidence of valvular insufficiency or dysfunction. The NOEL for valvulopathy in the rat is 50 mg/kg administered on a 2-weeks-on/2-weeks-off schedule and 8 mg/kg in the dog in the 6-month

study. In an effort to characterize the reversibility of cardiovascular lesions, a non-good laboratory practice (GLP) study in rats administered 250 mg/kg daily for 8 weeks followed by a 6-week recovery period was conducted. Data indicate that vascular lesions are partially reversible when rats are administered a dose known to induce a high incidence of cardiovascular lesions (vasculitis and valvulopathy) with daily dosing. After the 6-week recovery period, a decrease in both incidences in severity of cardiovascular lesions was observed. However, at the end of this recovery period, a few animals still were observed with minimal-to-moderate inflammation at the base of the aorta, coronary arteries or valves, and minimal stromal hyperplasia of the atrioventricular valves. These lesions were still considered adverse.

Treatment with LY2157299 results in a continuum of changes characterized by inflammation in the mucosa of mid- and high-dose (150 and 250 mg/kg) rats dosed either daily or intermittently for 3 months to proliferative changes at the mid and high dose (150 and 250 mg/kg) in the 6-month daily-dosing rat study. The proliferative changes included simple mucosal hyperplasia that progressed to include adenomatous hyperplasia, adenoma, and, in 2 males at the high dose, adenocarcinoma.

In the rat, additional important compound-related findings affecting the skeletal system, consisting of proliferation of trabecular bone or sternal cartilage, altered endochondral ossification, and slightly increased degeneration of articular cartilage were observed. Consistent with literature predictions (Lahn et al. 2005), administration of LY2157299 in a pilot embryo-fetal study resulted in increased resorptions and fetal skeletal morphology at 20 and 200 mg/kg. A no effect level for embryo-fetal effects was established at 2 mg/kg in this pilot study. In the dog, corneal edema and episcleritis were noted in the eyes of dogs at the high dose (60 mg/kg) during a scheduled ophthalmologic examination of all dogs on Day 176. Corneal endothelitis (inflammation of the most posterior cell layer of the cornea) was considered to be the primary change. Histologic evaluation of the eye was unremarkable. Additional important compound-related findings in the dog consisted of atrophy and/or inflammation of the mucosa of the stomach and large intestine, proliferation of sterna cartilage, and gallbladder mucification.

For additional information, see Section 5 in the IB.

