5.1.7. Rationale for Amendment (b)

The protocol is amended for the following reasons:

As part of the continuous monitoring of safety, PK, and laboratory markers in patients with HCC, the sponsor noted that patients are staying on study beyond 4 months. Furthermore, the 300 mg/day dose appears to have no evidence of increased toxicity. There appears to be no difference in the number of patients at the 160-mg/day and the 300-mg/day dose who stayed beyond 4 months. In addition, in all other ongoing trials with LY2157299, the dose of 300 mg/day was selected for future clinical development.

Preliminary PK data from the first interim analysis (n=20 patients) suggest that patients administered 300 mg/day have higher exposures than previously observed for the same dose level (Study JBAH) during the treatment period. LY2157299 appears to be fully eliminated after the 14-days off period of a cycle (additional PK sampling is added to study the clearance of LY2157299). The lowest exposure level (ie, most conservative) in the most sensitive nonclinical species administered LY2157299 in a clinically relevant dosing schedule (2 weeks on/2 weeks off) in which cardiac effects were observed was 24 $\mu\text{g}\cdot\text{hr}/\text{mL}$ (Table JBAK.2). The findings at this dose level (150 mg/kg) consisted of a single male rat (n=10/group) with minimal inflammation in the aortic valve and ascending aorta. Administration of 300 mg/day to patients with HCC may result in higher than anticipated exposures; however, due to the clinical safety profile observed thus far and the benefit:risk in this patient population, this approach is considered acceptable.

Because of these reasons and the lack of substantial evidence that the 160-mg/day dose is superior to the 300-mg/day dose, the dose of 300 mg/day is selected for the continuation of this trial.

For Part B, it was decided to evaluate the effects of LY2157299 in patients with AFP <1.5x upper limit of normal (ULN) to have an overall assessment of LY2157299 efficacy in all HCC patients. At the time of the decision to focus on the 300-mg/day dose, 74 patients were randomized.

The study design will be modified as follows:

- Part A: Evaluation of LY2157299 in Child-Pugh A or B7 patients with AFP $\geq 1.5x$ ULN. After stopping the 160-mg/day dose arm, all newly enrolled patients will be treated at the 300-mg/day dose.
- Part B: Evaluation of LY2157299 in Child-Pugh A or B7 patients with AFP <1.5x ULN

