Attachment 1. Protocol JBAK Study Schedule

Parts A and B

Cycle/Visit ^j	Prestudy			Cycle 1					Cycle 2		Cycle 3, n ^l		Extension Period	Visit 801	Follow-up ^f	Comments
	≤28	≤14	≤7	1 ⁱ	8 ⁱ	14 ⁱ	15	22	1 ⁱ	14 ^{i,k}	1 ⁱ	14 ^{i,k}				
Procedures																
Informed Consent	X															Informed consent must be signed prior to performing any study procedures.
Medical History		X														
Child-Pugh, Barcelona Clinic Liver Cancer (BCLC), and CLIP staging			X ^h													
Pregnancy Test			X													
Physical Exam		X		X		X			X	X	X		X	X		Starting in Cycle 3, to be performed once per cycle. Perform predose on Day 1 of each cycle in extension period.
Vital Signs (heart rate, blood pressure)		X		X		X			X	X	X		X	X		Starting in Cycle 3, to be performed once per cycle. Perform predose on Day 1 of each cycle in extension period.
CTCAE Grading		X		X		X			X	X	X		X	X	X ^a	Starting in Cycle 3, to be performed once per cycle. Perform predose on Day 1 of each cycle in extension period.
Concomitant Medications		X		X					X		X		X	X	X	Perform predose on Day 1 of each cycle in extension period.
Performance Status		X		X		X			X	X	X		X	X		Starting in Cycle 3, to be performed once per cycle. Perform predose on Day 1 of each cycle in extension period.

Cycle/Visitj	Prestudy			Cycle 1					Cycle 2		Cycle 3, n ^l		Extension Period	Visit 801	Follow-up ^f	Comments
	≤28	≤14	≤7	1 ⁱ	8 ⁱ	14 ⁱ	15	22	1 ⁱ	14 ^{i,k}	1 ⁱ	14 ^{i,k}				
Tumor Assessment, Physical (Palpable or Visible)		X		X					X		X			X		Optional during the extension period (including extension period V801)
Imaging Procedures																
Echocardiography with Doppler ^g	X								X		X		X	X ^b	X ^b	Cycle 2, 3, 4, and every other cycle (C6, C8,...etc). Perform predose on Day 1 of each cycle in extension period
Chest CT Scan or Chest MRI		X											X	X ^c		CT scan or MRI every 6 months
Tumor Assessment, Radiological		X								X	X			X ^d	X ^d	Tumor assessment every 6 weeks starting Cycle 2, Day 14. May be performed 3 days around the scheduled date. Optional during the extension period (including extension period V801)
ECG		X							X		X		X	X ^b	X ^b	Cycle 2, 3, 4, and every other cycle (C6, C8,...etc). Perform predose on Day 1 of each cycle in extension period

Cycle/Visit ^j	Prestudy			Cycle 1					Cycle 2		Cycle 3, n ^l		Extension Period	Visit 801	Follow-up ^f	Comments
	≤28	≤14	≤7	1 ⁱ	8 ⁱ	14 ⁱ	15	22	1 ⁱ	14 ⁱ , k	1 ⁱ	14 ⁱ , k				
Laboratory /Diagnostic Tests																

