Abbreviations: AFP = alpha-fetoprotein; aPTT = activated partial prothrombin time; C = cycle; CLIP = Cancer of the Liver Italian Program; CT = computerized tomography; CTCAE = Common Terminology Criteria for Adverse Events; ECG = electrocardiogram; FACT = Functional Assessment of Cancer Therapy; INR = international normalized ratio; MAP = multi-analyte panel; MRI = magnetic resonance imaging; PGx = pharmacogenomics; PIVKA II = prothrombin induced by vitamin K absence; PK = pharmacokinetic; PT = prothrombin time; TGF-β = transforming growth factor beta.

- a If drug-related toxicity is present 30 days after last cycle of study drug, patients must be followed up approximately every 30 days until toxicity resolution, stabilization, another therapy is initiated, or death.
- b If the patient has clinically significant cardiac findings at discontinuation (V801), echocardiography with Doppler, ECG, and ECG chemistry will be repeated every 2 months for 6 months (V803, V804, and V805). If there are no cardiac findings at discontinuation (V801), 1 more echocardiography with Doppler, ECG, and ECG chemistry will be performed after 2 months (V802) unless a patient is receiving another treatment (see Section 10.2.4).
- c If there were no clinically significant findings at the last assessment conducted within the 30 days following discontinuation and the patient has started another treatment, Visit 801 CT scan or chest MRI with contrast will not be performed.
- d Repeat radiological scans at study discontinuation may be omitted if a patient has objective disease progression or if imaging has been performed in the previous 3 to 6 weeks.
- e For details, see Attachment 4. PK sampling will be performed on Cycle 1, with a predose sample on Day 1 of Cycle 2 and all subsequent cycles.
- f Follow-up consists of Visit 802 and all subsequent visits (60 days ±7 days)
- g Echocardiography with Doppler can be performed up to 3 days prior to Day 1.
- h Child-Pugh, BCLC, and CLIP assessment procedures can be found in Attachment 5, Attachment 6, and Attachment 7, respectively.
- i To be performed predose LY2157299.
- j A delay at the start of a cycle (Day 1) of no more than 3 days, because of holidays, weekends, inclement weather, or other justifiable events, will be permitted and not counted as a protocol violation.
- k In extenuating circumstances, the ‘on study drug’ window is allowable from Day 10 to Day 14.

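### LY2157299's named blood pressure and heart rate effect is left to clinic monitoring, yet every scheduled on-treatment vital sign is predose, so none falls near peak concentration

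*Protocol*

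**What the plan says.** Protocol section 5.1.4 reports from safety pharmacology that LY2157299 "may produce dose-dependent hemodynamic side effects, measured by decreased blood pressure and increases in heart rate, which can be easily monitored in the clinic". The same sentence adds that the effect reverses when treatment stops.

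Attachment 1 has a row for "Vital Signs (heart rate, blood pressure" in the schedule of every Part. It is marked at screening, on Cycle 1 Days 1 and 14, on Cycle 2 Days 1 and 14, on Day 1 of later cycles, in the extension period and at Visit 801. The Day 1 and Day 14 columns carry footnote i: "To be performed predose LY2157299" (Parts C and D add the partner drug). The row's comment reads "Starting in Cycle 3, to be performed once per cycle. Perform predose on Day 1 of each cycle in extension period".

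On pharmacokinetics, section 5.1.3 says the median time to peak at steady state "ranged from 0.5 to 2 hours postdose, independent of dose". Section 5.1.7 says that "LY2157299 appears to be fully eliminated after the 14-days off period of a cycle".

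SAP section 5.3.9.7 plans only a listing of vital signs, and heart rate is not among the variables it names. That SAP is aligned with Amendment (c) and does not cover Parts D and E.

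**The concern.** The protocol names a blood pressure and heart rate effect and relies on clinic monitoring to see it. The scheduled readings are then all taken when drug concentration is at its lowest or zero. If the effect is largest around peak and causes no symptoms, the scheduled readings are poorly placed to show it.

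This matters most for Part E. Amendment (e) adds a third week of dosing, and no vital sign is scheduled on Days 15 to 21 of any cycle. Section 5.1.7 also reports higher exposure at 300 mg/day in HCC patients than was seen at that dose in Study JBAH.

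**Working it through.** There is no plan figure to reproduce. The check has two steps: where the readings fall, and how far trough lies below peak.

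**1. Position of scheduled readings over 6 cycles (Attachment 1)**

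| Reading | Number | Drug state |
|---|---|---|
| Cycle 1 Day 1, predose | 1 | before any drug |
| Day 1 of Cycles 2 to 6, predose | 5 | after 14 days off (7 in Part E) |
| Day 14 of Cycles 1 and 2, predose | 2 | about 12 h after the last dose |
| Near peak (0.5 to 2 h) | 0 | – |

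Total 1 + 5 + 2 = 8. From Cycle 3 on, every scheduled reading is off drug.

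In the text available to me the Part C row is misaligned, so its second Cycle 1 mark could belong to Day 8 or Day 14. Both columns are predose, so the count does not change.

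Other scheduled measurements do not fill the gap:
- Visit 801 begins the day after treatment stops (section 10).
- Blood pressure is recorded at echocardiography (Attachment 12), but on-study echocardiograms fall on Day 1, predose, or up to 3 days earlier, which is off drug.
- The PK row in Parts A, B and E is said to be timed with ECG, but the ECG row has no Cycle 1 mark. The two coincide only on Day 1 of later cycles, predose.

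**2. Trough relative to peak**

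Inputs from section 5.1.3: "The mean population clearance of LY2157299 was 38.4 L/h"; steady-state volume 193 L; peak at 0.5 to 2 h. The dosing interval is taken as 12 h.

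- k = CL/V = 38.4/193 = 0.199 per hour; half-life = ln 2/0.199 = 3.5 h.
- Trough/peak = exp(−k × (12 − tmax)).
- tmax 0.5 h: exp(−0.199 × 11.5) = 0.10. tmax 2 h: exp(−0.199 × 10) = 0.14.

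Check on the approximation: the implied accumulation ratio is 1/(1 − exp(−12k)) = 1.10. Section 5.1.3 gives a ratio "observed to be approximately 1", so the two agree.

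Sensitivity, using the nonclinical half-life of 4 to 8 h (section 5.1.1):
- 4 h: 0.14 to 0.18. 8 h: 0.37 to 0.42.
- An 8 h half-life would imply an accumulation ratio of 1.55, which fits the stated ratio poorly, so the upper end is a generous bound.

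Even with an 8 h half-life, the fraction left after 7 days off is 2^(−168/8) = 2^(−21), about 5 in 10 million. The Day 1 readings in Part E are therefore also off drug.

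**The case against.** The strongest reply is that section 5.1.4 is hedged nonclinical background. It says the effect depends on dose and is reversible; it gives no time course and no link to peak concentration. If the effect follows cumulative exposure or outlasts plasma levels, the Day 14 readings are informative. This stands: timing at peak is an inference. A reader might conclude that a real effect would look absent, or that the present readings cannot detect it. The documents do not support that, since drug at the Day 14 readings is 10% to 42% of peak on the figures above.

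The safety objective also does not rest on these readings alone. Adverse events are collected from the first dose, and clinically significant vital-sign findings leading to a diagnosis are reported (section 10.2.1). Blood pressure is to be monitored with ramucirumab in Part D (section 9.5.3.2) and checked regularly with sorafenib in Part C (section 9.5.2). These checks carry no time point and are tied to the partner drugs, but they mean the effect is unscheduled at peak rather than never measured.

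Clinical experience is reassuring. About 696 patients and 20 healthy subjects had been treated; neither hypotension nor tachycardia is among the adverse events reported at 10% or more (section 5.1.5.1), and the 745-patient cardiovascular review found no concerning adverse event trends (section 5.1.10). This lowers the urgency. It does not settle an asymptomatic effect: the data sources listed for that review do not include vital signs.

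Finally, new readings cannot recover a dose comparison. Parts A and B are complete, Part C is fully enrolled, Part E has one dose, and Part D may have as few as 3 patients at the lower dose. That is also correct, and it limits what the fix can claim.

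**Conclusion.** The point holds as a gap in scheduled measurement. Section 5.1.4 relies on clinic monitoring of a named effect, and Attachment 1 schedules 0 of 8 on-treatment readings near peak, with 2 at trough and 6 with no drug present (one of them the baseline). In Part E the third dosing week has none. An asymptomatic effect at peak, if one exists, would not be captured by scheduled readings.

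The count rests only on the schedule and its footnotes. The 10% to 14% figure assumes one compartment and a 12-hour interval; the protocol's model has two compartments and its other parameters are not given. Whether the effect tracks concentration is not stated.

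A reader might infer that the safety and dose-recommendation objectives fail for this reason. The documents do not support that: symptomatic events are still reported, and those objectives draw on other data. This is an inexpensive improvement worth making, not a flaw that undermines the trial.

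**What to change.** In Attachment 1, add heart rate and blood pressure at PK samples that already exist in Attachment 4:

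- **Part E:** at the 0.5 to 2 h sample on Cycle 1 Days 1 and 21. Day 21 also puts a reading in the third dosing week.
- **Part D, patients still to be enrolled (enrolment is already under way):** at the 0.5 h or 2 h sample on Cycle 1 Day 14, when no ramucirumab is given. Do not use Day 1: LY2157299 is taken within 30 minutes before a 60-minute infusion, so the 1.5 to 3 h sample falls at or after the end of the infusion and the reading would be confounded.

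Keep the existing predose readings, and take one before the dose on Part E Day 21, at the predose PK sample, if a same-day change is wanted there. In the SAP version covering Parts D and E, summarise change from predose descriptively by Part, name heart rate explicitly, and make no claim to a dose comparison.

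Cost: one or two extra post-dose cuff readings per patient at visits already attended (plus the optional Day 21 predose reading), and wording changes in Attachment 1 and the SAP. Limitation: neither Part has a control arm, so the change from predose includes ordinary time-of-day variation.
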